#### 7.4.6 Deaths

Separate summaries for on-treatment death and all deaths (*including* on-treatment and post-treatment) will be produced by primary system organ class and preferred term overall using the Safety Set. On-treatment and all deaths will be listed overall, and post treatment deaths will be flagged.

Study Code: CLCI699C2X01B

## 8 ATTACHMENTS

### 8.1 LIST OF AES OF SPECIAL INTEREST

PT_NAME	PT_CODE	Safety Topic Of Interest
11-deoxycorticosterone increased	10081511	AESI Adrenal Hormone Precursor Accumulation-related AEs
11-deoxycortisol increased	10081510	AESI Adrenal Hormone Precursor Accumulation-related AEs
Acne	10000496	AESI Adrenal Hormone Precursor Accumulation-related AEs
Acquired apparent mineralocorticoid excess	10080230	AESI Adrenal Hormone Precursor Accumulation-related AEs
Androgenetic alopecia	10068168	AESI Adrenal Hormone Precursor Accumulation-related AEs
Androgens increased	10002265	AESI Adrenal Hormone Precursor Accumulation-related AEs
Blood potassium decreased	10005724	AESI Adrenal Hormone Precursor Accumulation-related AEs
Blood pressure diastolic increased	10005739	AESI Adrenal Hormone Precursor Accumulation-related AEs
Blood pressure increased	10005750	AESI Adrenal Hormone Precursor Accumulation-related AEs
Blood pressure systolic increased	10005760	AESI Adrenal Hormone Precursor Accumulation-related AEs
Blood sodium increased	10005803	AESI Adrenal Hormone Precursor Accumulation-related AEs
Blood testosterone free increased	10053785	AESI Adrenal Hormone Precursor Accumulation-related AEs
Blood testosterone increased	10005815	AESI Adrenal Hormone Precursor Accumulation-related AEs
Endocrine hypertension	10057615	AESI Adrenal Hormone Precursor Accumulation-related AEs
Generalised oedema	10018092	AESI Adrenal Hormone Precursor Accumulation-related AEs
Hair growth abnormal	10019044	AESI Adrenal Hormone Precursor Accumulation-related AEs
Hirsutism	10020112	AESI Adrenal Hormone Precursor Accumulation-related AEs
Hydroxycorticosteroids increased	10020534	AESI Adrenal Hormone Precursor Accumulation-related AEs
Hydroxycorticosteroids urine increased	10020539	AESI Adrenal Hormone Precursor Accumulation-related AEs
Hyperandrogenism	10065597	AESI Adrenal Hormone Precursor Accumulation-related AEs
Hypernatraemia	10020679	AESI Adrenal Hormone Precursor Accumulation-related AEs

Study Code: CLCI699C2X01B

PT_NAME	PT_CODE	Safety Topic Of Interest
Hypertension	10020772	AESI Adrenal Hormone Precursor Accumulation-related AEs
Hypertrichosis	10020864	AESI Adrenal Hormone Precursor Accumulation-related AEs
Hypokalaemia	10021015	AESI Adrenal Hormone Precursor Accumulation-related AEs
Hypokalaemic syndrome	10021017	AESI Adrenal Hormone Precursor Accumulation-related AEs
Localised oedema	10048961	AESI Adrenal Hormone Precursor Accumulation-related AEs
Oedema	10030095	AESI Adrenal Hormone Precursor Accumulation-related AEs
Oedema peripheral	10030124	AESI Adrenal Hormone Precursor Accumulation-related AEs
Cardiac arrest	10007515	AESI Arrhythmogenic potential AEs
Cardiac death	10049993	AESI Arrhythmogenic potential AEs
Cardiac fibrillation	10061592	AESI Arrhythmogenic potential AEs
Cardio-respiratory arrest	10007617	AESI Arrhythmogenic potential AEs
Loss of consciousness	10024855	AESI Arrhythmogenic potential AEs
Sudden cardiac death	10049418	AESI Arrhythmogenic potential AEs
Sudden death	10042434	AESI Arrhythmogenic potential AEs
Syncope	10042772	AESI Arrhythmogenic potential AEs
Torsade de pointes	10044066	AESI Arrhythmogenic potential AEs
Ventricular arrhythmia	10047281	AESI Arrhythmogenic potential AEs
Ventricular fibrillation	10047290	AESI Arrhythmogenic potential AEs
Ventricular flutter	10047294	AESI Arrhythmogenic potential AEs
Ventricular tachyarrhythmia	10065341	AESI Arrhythmogenic potential AEs
Ventricular tachycardia	10047302	AESI Arrhythmogenic potential AEs
Addison's disease	10001130	AESI Hypocortisolism related AEs
Adrenal insufficiency	10001367	AESI Hypocortisolism related AEs
Adrenal suppression	10001382	AESI Hypocortisolism related AEs
Adrenocortical insufficiency acute	10001389	AESI Hypocortisolism related AEs
Cortisol decreased	10011198	AESI Hypocortisolism related AEs
Cortisol free urine decreased	10011201	AESI Hypocortisolism related AEs
Glucocorticoid deficiency	10072079	AESI Hypocortisolism related AEs
Glucocorticoids decreased	10061466	AESI Hypocortisolism related AEs
Primary adrenal insufficiency	10052381	AESI Hypocortisolism related AEs
Secondary adrenocortical insufficiency	10039807	AESI Hypocortisolism related AEs
Steroid withdrawal syndrome	10042028	AESI Hypocortisolism related AEs
ACTH-producing pituitary tumour	10000613	AESI Pituitary tumor enlargement-related AEs
Cavernous sinus syndrome	10079769	AESI Pituitary tumor enlargement-related AEs
Chiasma syndrome	10067348	AESI Pituitary tumor enlargement-related AEs
Diplopia	10013036	AESI Pituitary tumor enlargement-related AEs
Extraocular muscle paresis	10015829	AESI Pituitary tumor enlargement-related AEs

Study Code: CLCI699C2X01B

PT_NAME	PT_CODE	Safety Topic Of Interest
III nerve disorder	10053644	AESI Pituitary tumor enlargement-related AEs
III nerve injury	10021281	AESI Pituitary tumor enlargement-related AEs
III nerve paralysis	10021283	AESI Pituitary tumor enlargement-related AEs
III nerve paresis	10054202	AESI Pituitary tumor enlargement-related AEs
IV nerve disorder	10065836	AESI Pituitary tumor enlargement-related AEs
IV nerve injury	10023108	AESI Pituitary tumor enlargement-related AEs
IV nerve paralysis	10023110	AESI Pituitary tumor enlargement-related AEs
IV nerve paresis	10054201	AESI Pituitary tumor enlargement-related AEs
Microvascular cranial nerve palsy	10079491	AESI Pituitary tumor enlargement-related AEs
Neoplasm progression	10061309	AESI Pituitary tumor enlargement-related AEs
Neoplasm recurrence	10061864	AESI Pituitary tumor enlargement-related AEs
Optic nerve compression	10076302	AESI Pituitary tumor enlargement-related AEs
Pituitary apoplexy	10056447	AESI Pituitary tumor enlargement-related AEs
Pituitary enlargement	10048675	AESI Pituitary tumor enlargement-related AEs
Pituitary haemorrhage	10049760	AESI Pituitary tumor enlargement-related AEs
Pituitary infarction	10035092	AESI Pituitary tumor enlargement-related AEs
Pituitary tumour	10035104	AESI Pituitary tumor enlargement-related AEs
Pituitary tumour benign	10061538	AESI Pituitary tumor enlargement-related AEs
Pituitary tumour recurrent	10057316	AESI Pituitary tumor enlargement-related AEs
Tumour compression	10068268	AESI Pituitary tumor enlargement-related AEs
Tumour invasion	10064390	AESI Pituitary tumor enlargement-related AEs
VI nerve disorder	10053646	AESI Pituitary tumor enlargement-related AEs
VI nerve injury	10047639	AESI Pituitary tumor enlargement-related AEs
VI nerve paralysis	10047641	AESI Pituitary tumor enlargement-related AEs
VI nerve paresis	10071044	AESI Pituitary tumor enlargement-related AEs
Visual field defect	10047555	AESI Pituitary tumor enlargement-related AEs
Electrocardiogram QT interval abnormal	10063748	AESI QT prolongation AEs
Electrocardiogram QT prolonged	10014387	AESI QT prolongation AEs
Long QT syndrome	10024803	AESI QT prolongation AEs

Study Code: CLCI699C2X01B

## 8.2 DATA FROM PARENT STUDIES

DATASET	VARIABLE	LENGTH	LABEL	ATTRIB
PR	STUDYID	200	Study Identifier	Character
PR	DOMAIN	200	Domain Abbreviation	Character
PR	USUBJID	200	Unique Subject Identifier	Character
PR	PRSEQ	8	Sequence Number	Numeric
PR	PRTRT	200	Reported Name of Procedure	Character
PR	PRCAT	200	Category	Character
PR	PRINDC	200	Indication	Character
PR	PRDOSE	8	Dose	Numeric
PR	PRDOSU	200	Dose Units	Character
PR	PRLOC	200	Location of Procedure	Character
PR	PRLAT	200	Laterality	Character
PR	VISITNUM	8	Visit Number	Numeric
PR	VISIT	200	Visit Name	Character
PR	VISITDY	8	Planned Study Day of Visit	Numeric
PR	EPOCH	200	Epoch	Character
PR	PRSTDTC	200	Start Date/Time of Procedure	Character
PR	PRENDTC	200	End Date/Time of Procedure	Character
PR	PRSTDY	8	Study Day of Start of Procedure	Numeric
PR	PRENDY	8	Study Day of End of Procedure	Numeric
FA	STUDYID	200	Study Identifier	Character
FA	DOMAIN	200	Domain Abbreviation	Character
FA	USUBJID	200	Unique Subject Identifier	Character
FA	FASEQ	8	Sequence Number	Numeric
FA	FATESTCD	200	Findings About Test Short Name	Character
FA	FATEST	200	Findings About Test Name	Character
FA	FAOBJ	200	Object of the Observation	Character
FA	FACAT	200	Category for Findings About	Character
FA	FAORRES	200	Result or Finding in Original Units	Character
FA	FAORRESU	200	Original Units	Character
FA	FASTRESC	200	Character Result/Finding in Std Format	Character
FA	FASTRESU	200	Standard Units	Character
FA	FASTSTAT	200	Completion Status	Character
FA	FAAREASND	200	Reason Not Performed	Character
FA	FAMETHOD	200	Method of Test or Examination	Character
FA	VISITNUM	8	Visit Number	Numeric
FA	VISIT	200	Visit Name	Character

Study Code: CLCI699C2X01B

DATASET	VARIABLE	LENGTH	LABEL	ATTRIB
FA	VISITDY	8	Planned Study Day of Visit	Numeric
FA	EPOCH	200	Epoch	Character
FA	FADTC	200	Date/Time of Collection	Character
FA	FADY	8	Study Day of Collection	Numeric
LB	STUDYID	200	Study Identifier	Character
LB	DOMAIN	200	Domain Abbreviation	Character
LB	USUBJID	200	Unique Subject Identifier	Character
LB	LBSEQ	8	Sequence Number	Numeric
LB	LBREFID	200	Specimen ID	Character
LB	LBTESTCD	200	Lab Test or Examination Short Name	Character
LB	LBTEST	200	Lab Test or Examination Name	Character
LB	LBCAT	200	Category for Lab Test	Character
LB	LBORRES	200	Result or Finding in Original Units	Character
LB	LBORRESU	200	Original Units	Character
LB	LBORNRL0	200	Reference Range Lower Limit in Orig Unit	Character
LB	LBORNRI0	200	Reference Range Upper Limit in Orig Unit	Character
LB	LBSTRESC	200	Character Result/Finding in Std Format	Character
LB	LBSTRESN	8	Numeric Result/Finding in Standard Units	Numeric
LB	LBSTRESU	200	Standard Units	Character
LB	LBSTNRLO	8	Reference Range Lower Limit-Std Units	Numeric
LB	LBSTNRHI	8	Reference Range Upper Limit-Std Units	Numeric
LB	LBSTNRC	200	Reference Range for Char Rslt-Std Units	Character
LB	LBNRIND	200	Reference Range Indicator	Character
LB	LBSTAT	200	Completion Status	Character
LB	LBREASND	200	Reason Test Not Done	Character
LB	LBNAME	200	Vendor Name	Character
LB	LBSPEC	200	Specimen Type	Character
LB	LBSPCCND	200	Specimen Condition	Character
LB	LBMETHOD	200	Method of Test or Examination	Character
LB	LBBFL	200	Baseline Flag	Character
LB	VISITNUM	8	Visit Number	Numeric
LB	VISIT	200	Visit Name	Character
LB	VISITDY	8	Planned Study Day of Visit	Numeric

Study Code: CLCI699C2X01B

DATASET	VARIABLE	LENGTH	LABEL	ATTRIB
LB	EPOCH	200	Epoch	Character
LB	LBDTC	200	Date/Time of Specimen Collection	Character
LB	LBENDTC	200	End Date/Time of Specimen Collection	Character
LB	LBDY	8	Study Day of Specimen Collection	Numeric
VS	STUDYID	200	Study Identifier	Character
VS	DOMAIN	200	Domain Abbreviation	Character
VS	USUBJID	200	Unique Subject Identifier	Character
VS	VSSEQ	8	Sequence Number	Numeric
VS	VSTESTCD	200	Vital Signs Test Short Name	Character
VS	VTEST	200	Vital Signs Test Name	Character
VS	VSORRES	200	Result or Finding in Original Units	Character
VS	VSORRESU	200	Original Units	Character
VS	VSSTRESC	200	Character Result/Finding in Std Format	Character
VS	VSSTRESN	8	Numeric Result/Finding in Standard Units	Numeric
VS	VSSTRESU	200	Standard Units	Character
VS	VSLFL	200	Baseline Flag	Character
VS	VISITNUM	8	Visit Number	Numeric
VS	VISIT	200	Visit Name	Character
VS	VISITDY	8	Planned Study Day of Visit	Numeric
VS	EPOCH	200	Epoch	Character
VS	VSDTC	200	Date/Time of Measurements	Character
VS	VSDY	8	Study Day of Vital Signs	Numeric
EG	STUDYID	200	Study Identifier	Character
EG	DOMAIN	200	Domain Abbreviation	Character
EG	USUBJID	200	Unique Subject Identifier	Character
EG	EGSEQ	8	Sequence Number	Numeric
EG	EGTESTCD	200	ECG Test or Examination Short Name	Character
EG	EGTEST	200	ECG Test or Examination Name	Character
EG	EGCAT	200	Category for ECG	Character
EG	EGORRES	200	Result or Finding in Original Units	Character
EG	EGORRESU	200	Original Units	Character
EG	EGSTRESC	200	Character Result/Finding in Std Format	Character
EG	EGSTRESN	8	Numeric Result/Finding in Standard Units	Numeric
EG	EGSTRESU	200	Standard Units	Character
EG	EGMETHOD	200	Method of ECG Test	Character
EG	EGLFL	200	Baseline Flag	Character

Study Code: CLCI699C2X01B

DATASET	VARIABLE	LENGTH	LABEL	ATTRIB
EG	VISITNUM	8	Visit Number	Numeric
EG	VISIT	200	Visit Name	Character
EG	VISITDY	8	Planned Study Day of Visit	Numeric
EG	EPOCH	200	Epoch	Character
EG	EGDTC	200	Date/Time of ECG	Character
EG	EGDY	8	Study Day of ECG	Numeric

Study Code: CLCI699C2X01B

### 8.3 GRADING FOR LAB TESTS (V5.0)

CTCAE Term	Grade 1	Grade 2	Grade 3	Grade 4	Grade 5
Hypoalbuminemia	<LLN - 3 g/dL; <LLN - 30 g/L	<3 - 2 g/dL; <30 - 20 g/L	<2 g/dL; <20 g/L	Life-threatening consequences; urgent intervention indicated	Death
Alanine aminotransferase increased	>ULN - 3.0 x ULN if baseline was normal; 1.5 - 3.0 x baseline if baseline was abnormal	>3.0 - 5.0 x ULN if baseline was normal; >3.0 - 5.0 x baseline if baseline was abnormal	>5.0 - 20.0 x ULN if baseline was normal; >5.0 - 20.0 x baseline if baseline was abnormal	>20.0 x ULN if baseline was normal; >20.0 x baseline if baseline was abnormal	-
Alkaline phosphatase increased	>ULN - 2.5 x ULN if baseline was normal; 2.0 - 2.5 x baseline if baseline was abnormal	>2.5 - 5.0 x ULN if baseline was normal; >2.5 - 5.0 x baseline if baseline was abnormal	>5.0 - 20.0 x ULN if baseline was normal; >5.0 - 20.0 x baseline if baseline was abnormal	>20.0 x ULN if baseline was normal; >20.0 x baseline if baseline was abnormal	-
Aspartate aminotransferase increased	>ULN - 3.0 x ULN if baseline was normal; 1.5 - 3.0 x baseline if baseline was abnormal	>3.0 - 5.0 x ULN if baseline was normal; >3.0 - 5.0 x baseline if baseline was abnormal	>5.0 - 20.0 x ULN if baseline was normal; >5.0 - 20.0 x baseline if baseline was abnormal	>20.0 x ULN if baseline was normal; >20.0 x baseline if baseline was abnormal	-
Serum amylase increased	>ULN - 1.5 x ULN	>1.5 - 2.0 x ULN; >2.0 - 5.0 x ULN and asymptomatic	>2.0 - 5.0 x ULN with signs or symptoms; >5.0 x ULN and asymptomatic	>5.0 x ULN and with signs or symptoms	-
Hypercalcemia	Corrected serum calcium of >ULN - 11.5 mg/dL; >ULN - 2.9 mmol/L; Ionized calcium >ULN - 1.5 mmol/L	Corrected serum calcium of >11.5 - 12.5 mg/dL; >2.9 - 3.1 mmol/L; Ionized calcium >1.5 - 1.6 mmol/L; symptomatic	Corrected serum calcium of >12.5 - 13.5 mg/dL; >3.1 - 3.4 mmol/L; Ionized calcium >1.6 - 1.8 mmol/L; hospitalization indicated	Corrected serum calcium of >13.5 mg/dL; >3.4 mmol/L; Ionized calcium >1.8 mmol/L; life-threatening consequences	Death

Study Code: CLCI699C2X01B

Definition: A disorder characterized by laboratory test results that indicate an elevation in the concentration of calcium (corrected for albumin) in blood.					
Hypocalcemia	Corrected serum calcium of <LLN - 8.0 mg/dL; <LLN - 2.0 mmol/L; Ionized calcium <LLN - 1.0 mmol/L	Corrected serum calcium of <8.0 - 7.0 mg/dL; <2.0 - 1.75 mmol/L; Ionized calcium <1.0 - 0.9 mmol/L; symptomatic	Corrected serum calcium of <7.0 - 6.0 mg/dL; <1.75 - 1.5 mmol/L; Ionized calcium <0.9 - 0.8 mmol/L; hospitalization indicated	Corrected serum calcium of <6.0 mg/dL; <1.5 mmol/L; Ionized calcium <0.8 mmol/L; life-threatening consequences	Death
CPK increased	>ULN - 2.5 x ULN	>2.5 x ULN - 5 x ULN	>5 x ULN - 10 x ULN	>10 x ULN	-
Definition: A finding based on laboratory test results that indicate an increase in levels of creatine phosphokinase in a blood specimen.					
Creatinine increased	>ULN - 1.5 x ULN	>1.5 - 3.0 x baseline; >1.5 - 3.0 x ULN	>3.0 x baseline; >3.0 - 6.0 x ULN	>6.0 x ULN	-
Definition: A finding based on laboratory test results that indicate increased levels of creatinine in a biological specimen.					
GGT increased	>ULN - 2.5 x ULN if baseline was normal; 2.0 - 2.5 x baseline if baseline was abnormal	>2.5 - 5.0 x ULN if baseline was normal; >2.5 - 5.0 x baseline if baseline was abnormal	>5.0 - 20.0 x ULN if baseline was normal; >5.0 - 20.0 x baseline if baseline was abnormal	>20.0 x ULN if baseline was normal; >20.0 x baseline if baseline was abnormal	-
Definition: A finding based on laboratory test results that indicate higher than normal levels of the enzyme gamma-glutamyltransferase in the blood specimen. GGT (gamma-glutamyltransferase) catalyzes the transfer of a gamma glutamyl group from a gamma glutamyl peptide to another peptide, amino acids or water.					
Lipase increased	>ULN - 1.5 x ULN	>1.5 - 2.0 x ULN; >2.0 - 5.0 x ULN and asymptomatic	>2.0 - 5.0 x ULN with signs or symptoms; >5.0 x ULN and asymptomatic	>5.0 x ULN and with signs or symptoms	-
Definition: A finding based on laboratory test results that indicate an increase in the level of lipase in a biological specimen.					
Hypermagnesemia	>ULN - 3.0 mg/dL; >ULN - 1.23 mmol/L	-	>3.0 - 8.0 mg/dL; >1.23 - 3.30 mmol/L	>8.0 mg/dL; >3.30 mmol/L; life-threatening consequences	Death
Definition: A disorder characterized by laboratory test results that indicate an elevation in the concentration of magnesium in the blood.					
Hypomagnesemia	<LLN - 1.2 mg/dL; <LLN - 0.5 mmol/L	<1.2 - 0.9 mg/dL; <0.5 - 0.4 mmol/L	<0.9 - 0.7 mg/dL; <0.4 - 0.3 mmol/L	<0.7 mg/dL; <0.3 mmol/L; life-threatening consequences	Death
Definition: A disorder characterized by laboratory test results that indicate a low concentration of magnesium in the blood.					
Hyperkalemia	>ULN - 5.5 mmol/L	>5.5 - 6.0 mmol/L; intervention initiated	>6.0 - 7.0 mmol/L; hospitalization indicated	>7.0 mmol/L; life-threatening consequences	Death

Study Code: CLCI699C2X01B

**Definition:** A disorder characterized by laboratory test results that indicate an elevation in the concentration of potassium in the blood; associated with kidney failure or sometimes with the use of diuretic drugs.

Hypokalemia	<LLN - 3.0 mmol/L	Symptomatic with <LLN - 3.0 mmol/L; intervention indicated	<3.0 - 2.5 mmol/L; hospitalization indicated	<2.5 mmol/L; life-threatening consequences	Death
-------------	-------------------	------------------------------------------------------------	----------------------------------------------	--------------------------------------------	-------

**Definition:** A disorder characterized by laboratory test results that indicate a low concentration of potassium in the blood.

Hypernatremia	>ULN - 150 mmol/L	>150 - 155 mmol/L; intervention initiated	>155 - 160 mmol/L; hospitalization indicated	>160 mmol/L; life-threatening consequences	Death
---------------	-------------------	-------------------------------------------	----------------------------------------------	--------------------------------------------	-------

**Definition:** A disorder characterized by laboratory test results that indicate an elevation in the concentration of sodium in the blood.

Hyponatremia	<LLN - 130 mmol/L	125-129 mmol/L and asymptomatic	125-129 mmol/L symptomatic; 120-124 mmol/L regardless of symptoms	<120 mmol/L; life-threatening consequences	Death
--------------	-------------------	---------------------------------	-------------------------------------------------------------------	--------------------------------------------	-------

**Definition:** A disorder characterized by laboratory test results that indicate a low concentration of sodium in the blood.

Blood bilirubin increased	>ULN - 1.5 x ULN if baseline was normal; > 1.0 - 1.5 x baseline if baseline was abnormal	>1.5 - 3.0 x ULN if baseline was normal; > 1.5 - 3.0 x baseline if baseline was abnormal	>3.0 - 10.0 x ULN if baseline was normal; >3.0 - 10.0 x baseline if baseline was abnormal	>10.0 x ULN if baseline was normal; >10.0 x baseline if baseline was abnormal	-
---------------------------	------------------------------------------------------------------------------------------	------------------------------------------------------------------------------------------	-------------------------------------------------------------------------------------------	-------------------------------------------------------------------------------	---

**Definition:** A finding based on laboratory test results that indicate an abnormally high level of bilirubin in the blood. Excess bilirubin is associated with jaundice.

Hemoglobin increased	Increase in >0 - 2 g/dL	Increase in >2 - 4 g/dL	Increase in >4 g/dL	-	-
----------------------	-------------------------	-------------------------	---------------------	---	---

**Definition:** A finding based on laboratory test results that indicate increased levels of hemoglobin above normal.

Anemia	Hemoglobin (Hgb) <LLN - 10.0 g/dL; <LLN - 6.2 mmol/L; <LLN - 100 g/L	Hgb <10.0 - 8.0 g/dL; <6.2 - 4.9 mmol/L; <100 - 80g/L	Hgb <8.0 g/dL; <4.9 mmol/L; <80 g/L; transfusion indicated	Life-threatening consequences; urgent intervention indicated	Death
--------	----------------------------------------------------------------------	-------------------------------------------------------	------------------------------------------------------------	--------------------------------------------------------------	-------

**Definition:** A disorder characterized by a reduction in the amount of hemoglobin in 100 ml of blood. Signs and symptoms of anemia may include pallor of the skin and mucous membranes, shortness of breath, palpitations of the heart, soft systolic murmurs, lethargy, and fatigability.

White blood cell decreased	<LLN - 3000/mm3; <LLN - 3.0 x 10e9 /L	<3000 - 2000/mm3; <3.0 - 2.0 x 10e9 /L	<2000 - 1000/mm3; <2.0 - 1.0 x 10e9 /L	<1000/mm3; <1.0 x 10e9 /L	-
----------------------------	---------------------------------------	----------------------------------------	----------------------------------------	---------------------------	---

**Definition:** A finding based on laboratory test results that indicate an decrease in number of white blood cells in a blood specimen.

Leukocytosis	-	-	>100,000/mm3	Clinical manifestations of leucostasis; urgent intervention indicated	Death
--------------	---	---	--------------	-----------------------------------------------------------------------	-------

---

Study Code: CLCI699C2X01B

**Definition:** A disorder characterized by laboratory test results that indicate an increased number of white blood cells in the blood.

**Navigational Note:** -

Lymphocyte count decreased	<LLN - 800/mm  ; <LLN - 0.8 x 10  /L	<800 - 500/mm  ; <0.8 - 0.5 x 10  /L	<500 - 200/mm  ; <0.5 - 0.2 x 10  /L	<200/mm  ; <0.2 x 10  /L	-
----------------------------	--------------------------------------------------------------	--------------------------------------------------------------	--------------------------------------------------------------	--------------------------------------------------	---

**Definition:** A finding based on laboratory test results that indicate a decrease in number of lymphocytes in a blood specimen.

**Navigational Note:** -

Lymphocyte count increased	-	>4000/mm  - 20,000/mm 	>20,000/mm 	-	-
----------------------------	---	------------------------------------------------	-------------------------	---	---

**Definition:** A finding based on laboratory test results that indicate an abnormal increase in the number of lymphocytes in the blood, effusions or bone marrow.

**Navigational Note:** -

Neutrophil count decreased	<LLN - 1500/mm  ; <LLN - 1.5 x 10  /L	<1500 - 1000/mm  ; <1.5 - 1.0 x 10  /L	<1000 - 500/mm  ; <1.0 - 0.5 x 10  /L	<500/mm  ; <0.5 x 10  /L	-
----------------------------	---------------------------------------------------------------	----------------------------------------------------------------	---------------------------------------------------------------	--------------------------------------------------	---

**Definition:** A finding based on laboratory test results that indicate a decrease in number of neutrophils in a blood specimen.

**Navigational Note:** -

Platelet count decreased	<LLN - 75,000/mm  ; <LLN - 75.0 x 10  /L	<75,000 - 50,000/mm  ; <75.0 - 50.0 x 10  /L	<50,000 - 25,000/mm  ; <50.0 - 25.0 x 10  /L	<25,000/mm  ; <25.0 x 10  /L	-
--------------------------	------------------------------------------------------------------	----------------------------------------------------------------------	----------------------------------------------------------------------	------------------------------------------------------	---

**Definition:** A finding based on laboratory test results that indicate a decrease in number of platelets in a blood specimen.

**Navigational Note:** -

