#### 7.4.2 Laboratory parameters

Laboratory data summaries will include all assessments available for the lab parameters collected no later than 30 days of safety follow-up whichever is later after the last study treatment administration date using data from all sources. All laboratory assessments will be listed and those collected later than 30 days after the last study treatment date will be flagged in the listings.

Grading of laboratory values will be assigned programmatically as per NCI Common Terminology Criteria for Adverse Events (CTCAE) version 4.03 or higher. The calculation of CTCAE grades will be based on the observed laboratory values only, clinical assessments will not be taken into account. CTCAE version 5.0 will be applied and an extract of the tests that can be graded is reported in attachment 8.3.

CTCAE Grade 0 will be assigned for all non-missing values not graded as 1 or higher. Grade 5 will not be used. For laboratory tests that are graded for both low and high values, summaries will be done separately and labeled by direction, e.g., sodium will be summarized as hyponatremia and hypernatremia.

---

Study Code: CLCI699C2X01B

For laboratory tests where grades are not defined by CTCAE, results will be categorized as low/normal/high based on laboratory normal ranges.

For laboratory tests where grades are defined by CTCAE:

- Summary table for AEs of grades 3 or 4
- Shift tables using CTCAE grades to compare baseline to the worst on-treatment value
- Worst post-baseline CTCAE grade (regardless of the baseline status). Each patient will be counted only once for the worst grade observed post-baseline

For laboratory tests where grades are not defined by CTCAE,

- Shift tables using the low/normal/high/ (low and high) classification to compare baseline to the worst on-treatment value

The following listings will be produced for the laboratory data (hematology, and biochemistry):

- Listing of all laboratory data with values flagged to show the corresponding CTC grades the classifications relative to the laboratory reference ranges
- Listing of notable laboratory abnormalities (i.e., CTC grade 3 or 4 laboratory toxicities).

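### For five liver tests the SAP grades against an elevated on-drug baseline, which raises the Grade 3 threshold and leaves the baseline-to-worst shift table unable to do its job

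*SAP*

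**What the plan says.** SAP 7.4.2 settles the grading scale: "CTCAE version 5.0 will be applied and an extract of the tests that can be graded is reported in attachment 8.3". In attachment 8.3, ALT, AST, ALP, GGT and bilirubin each have two branches, one in multiples of ULN and one in multiples of the patient's own baseline.

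- ALT/AST Grade 1: ">ULN - 3.0 x ULN if baseline was normal; 1.5 - 3.0 x baseline if baseline was abnormal".
- ALP/GGT Grade 1, abnormal-baseline branch: "2.0 - 2.5 x baseline if baseline was abnormal".
- ALT, AST, ALP and GGT Grade 3: ">5.0 - 20.0 x ULN if baseline was normal; >5.0 - 20.0 x baseline if baseline was abnormal".
- Bilirubin Grade 3, abnormal-baseline branch: ">3.0 - 10.0 x baseline if baseline was abnormal".

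SAP 4.1.1 takes baseline from the End of Treatment visit of the parent study. Protocol 5.1 requires patients to be receiving osilodrostat in that study when they roll over.

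The outputs built on these grades in SAP 7.4.2 include "Shift tables using CTCAE grades to compare baseline to the worst on-treatment value", a worst post-baseline grade table, and "Listing of notable laboratory abnormalities (i.e., CTC grade 3 or 4 laboratory toxicities". SAP Table 5-1 names shift tables against baseline and the proportions with notable or Grade 3/4 values as the analysis of the secondary safety data. The only default for ungraded values is "CTCAE Grade 0 will be assigned for all non-missing values not graded as 1 or higher". Nothing says which branch grades the baseline record, and nothing defines an abnormal baseline.

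**The concern.** The reference value is itself an on-drug measurement. A liver elevation already present at roll-over raises the threshold for every later value of that test. High values can then fall short of Grade 3 and be left out of the outputs that Table 5-1 relies on.

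The shift table raises a second issue. It needs a baseline grade and a worst on-treatment grade on one scale that can show both entry status and change. With no rule for the baseline record, two programmers could follow the SAP and produce different tables. At stake is the summary of liver laboratory safety for patients who enter with an elevated test, in a study whose purpose is long-term safety.

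**Working it through.** **Inputs**

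- Lower limits of Grades 1/2/3/4 from SAP 8.3. ULN branch: ALT/AST 1, 3, 5, 20; ALP/GGT 1, 2.5, 5, 20; bilirubin 1, 1.5, 3, 10. Baseline branch: the same multiples applied to baseline, except that Grade 1 starts at 1.5 (ALT/AST), at 2.0 (ALP/GGT) and above 1.0 (bilirubin).
- Grade 0 default: SAP 7.4.2.
- Baseline level b, in multiples of ULN: not in the documents. I assume 1.2 to 4.

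The plan gives no figure to reproduce. As a check, b = 1 returns the printed Grade 3 limits of 5 and 3.

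**Step 1: the Grade 3 threshold.** Let x be the later value in multiples of ULN and r = x/b. For b > 1, Grade 3 needs r > 5, that is x > 5b (bilirubin r > 3, x > 3b). Values in (5, 5b], or (3, 3b] for bilirubin, are Grade 3 or higher on ULN multiples but below Grade 3 in the SAP.

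| b | ALT/AST/ALP/GGT: Grade 3 above | Bilirubin: Grade 3 above |
|---|---|---|
| 1 | 5 | 3 |
| 1.2 | 6 | 3.6 |
| 1.5 | 7.5 | 4.5 |
| 2 | 10 | 6 |
| 2.5 | 12.5 | 7.5 |
| 3 | 15 | 9 |
| 4 | 20 | 12 |

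Example: ALT from 2.5 to 12 x ULN gives r = 12/2.5 = 4.8, so Grade 2. An isolated ALT of 12 x ULN lies in the >10 x ULN row of protocol Table 6-3.

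**Step 2: baseline record, literal reading.** Graded by its own row, the baseline has r = 1. That is below 1.5 (ALT/AST), below 2.0 (ALP/GGT) and not above 1.0 (bilirubin), so an elevated baseline takes the Grade 0 default. A normal baseline is Grade 0 too. Every patient therefore starts at Grade 0, and the table only repeats the distribution of worst grades.

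**Step 3: baseline record graded on ULN.** The baseline is then on one scale and the worst value on another.

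| Baseline to worst (x ULN) | r | Literal | Baseline on ULN, worst by 8.3 | ULN for both |
|---|---|---|---|---|
| ALT 2 to 2 | 1 | 0 to 0 | 1 to 0 | 1 to 1 |
| ALT 4 to 4 | 1 | 0 to 0 | 2 to 0 | 2 to 2 |
| ALT 4 to 8 | 2 | 0 to 1 | 2 to 1 | 2 to 3 |
| ALT 2.5 to 12 | 4.8 | 0 to 2 | 1 to 2 | 1 to 3 |
| ALP or GGT 3 to 5.9 | 1.97 | 0 to 0 | 2 to 0 | 2 to 3 |
| Bilirubin 2 to 2.8 | 1.4 | 0 to 1 | 2 to 1 | 2 to 2 |
| Bilirubin 1.5 to 4.4 | 2.93 | 0 to 2 | 1 to 2 | 1 to 3 |

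In the mixed-scale column, any ALT/AST rise below 50% from an elevated baseline (ALP/GGT below 100%) shows as a fall to Grade 0.

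**Step 4: meaning of abnormal.** The threshold rises only if b > 1. If a value below the lower limit also counted as abnormal, the threshold would fall. With an assumed ALP baseline of 0.3 x ULN, Grade 1 starts at 2.0 x 0.3 = 0.6 x ULN, inside the normal range, and Grade 3 above 5 x 0.3 = 1.5 x ULN.

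**The case against.** The strongest reply is that grading against an abnormal baseline belongs to the v5.0 scale the SAP has chosen, and is a legitimate way to show change from entry. That stands. The baseline-relative grades need not be dropped; the weakness is using them alone, with an on-drug baseline.

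It is also fair that the literal reading is the more natural one, and that under it rises large enough to reach a grade point the right way. A reader might infer that the shift table reverses direction whichever way it is programmed. The documents do not support that. False improvement arises only if the baseline is graded on ULN, which no section prescribes; the literal reading is uninformative about entry status, not reversed.

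A reader might also infer that the SAP under-grades all five tests against limits the protocol acts on. That goes too far. Table 6-3 has action rows for isolated bilirubin and isolated AST/ALT, but none for ALP or GGT; ALP enters only through the cholestasis condition. For combined elevations with an elevated baseline, the protocol itself uses baseline multiples, with fixed ULN limits alongside.

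Other outputs carry part of the signal. All laboratory values are listed with reference-range classification, and dose interruptions, discontinuations and the related AEs are reported. These make single patients traceable but do not repair the summary tables. SAP 7.4.2 describes the worst-grade table as irrespective of baseline status, but the grade it tabulates still depends on baseline through attachment 8.3.

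**Conclusion.** The point holds as a cheap improvement. For an elevated baseline, Grade 3 starts at 5b x ULN (bilirubin 3b), and the shift table for these five tests cannot show entry status on the literal reading or mixes two scales on the other. The arithmetic rests only on attachment 8.3 and on b being above 1.

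The consequence is uncertain. The documents give no count of patients with an elevated liver test at roll-over; the number affected is unknown and may be zero. At b = 1.2 the lost windows are narrow (5 to 6, and 3 to 3.6 for bilirubin). No hypothesis is tested and the primary AE/SAE endpoint is unaffected, so it should not be inferred that the study's main safety conclusion is compromised.

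Protocol 12.5.1.3 names CTCAE v4.03 for laboratory grading, while SAP 7.4.2 allows 4.03 or higher and then applies v5.0. A reader might take this conflict as the source of the problem or as changing the counts. The v4.03 rules are not in the documents, so its effect cannot be worked out here; it is a side point to reconcile.

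**What to change.** In SAP 7.4.2, for ALT, AST, ALP, GGT and bilirubin:

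- Build the shift table on ULN multiples, using the normal-baseline cut-offs of attachment 8.3 for both the baseline and the post-baseline record.
- Show the worst-grade counts, the Grade 3/4 counts and the notable listing on ULN multiples beside the v5.0 grades, each labelled.
- State that an abnormal baseline means above ULN, and how the baseline record is graded under v5.0.
- Reconcile the CTCAE version with protocol 12.5.1.3.

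Counts of patients crossing the existing Table 6-3 limits could be added, but the point does not depend on them.

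The cost is SAP wording and a little programming. No new data are needed: the parent-study laboratory extract in SAP 8.2 already carries the upper reference limit. The downsides are two labelled sets of grades for five tests, and Grade 3/4 liver counts that may look slightly less favourable.
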